5. STUDY CONDUCT

5.1 Restrictions during the study

When applicable, WOCBP as defined in Section 4.1, must agree to use adequate contraception (adequate contraception can include abstinence if the investigator deems it appropriate) and must have a negative urine pregnancy test prior to the administration of the IP. A positive urine pregnancy test during the study, including at the final visit, will be followed by a serum pregnancy test for confirmation.

Use of concomitant medications is restricted as detailed in Section 5.6, [Table 6](#).

To ensure safety, all patients must refrain from driving and operating heavy machinery for the remainder of the day after infusions 1, 2, and 3 (Week 1). Patients who are unaccompanied by a driver will be provided transportation to their home. After Week 1, the investigator will determine the patient's ability to drive prior to leaving the site at every infusion visit. The investigator may restrict driving at any time should there be a safety concern, and provide alternative transportation for the patient.

5.2 Subject enrolment and randomisation

The principal investigator (PI) will:

1. Obtain signed informed consent from the potential patient before any study-specific procedures are performed.
2. Assign potential patient a unique enrollment number, beginning with “E#” (for example, E-1100-001).
3. Determine patient eligibility. See Sections [4.1](#) and [4.2](#).
4. Assign via Interactive Voice Response System (IVRS) an eligible patient unique randomization code (patient number), beginning with “#”.

As patients are screened for the study, they must be allocated an enrollment code (E-code). The E-code is a 7-digit number made up of the site number (4-digits) and the patient number within that particular site (3-digits) (for example, E-1100-001).

5.2.1 Procedures for randomisation

Eligible patients will be randomized in balanced blocks to receive AZD6765iv 50 mg or 100 mg, or placebo saline infusion in a 1:1:1 ratio. The actual treatment given to individual patients will be determined by a randomization scheme that has been loaded into the IVRS database. If a patient is discontinued from the study, his/her randomization or enrollment number will not be reused, and the patient will not be allowed to re-enter the study. Patients who discontinue from the study will not be replaced.

If a randomization number is allocated incorrectly, no attempt should be made to remedy the error once study material has been dispensed. The patient will continue with the allocated number and study material. AstraZeneca or representative should be notified as soon as the error is discovered. Subsequent patients will continue using the first unallocated randomization number in the original numbering sequence.

5.3 Procedures for handling subjects incorrectly enrolled or randomised

Patients who do not meet the inclusion/exclusion criteria for the study should not, under any circumstances, be enrolled. There can be no exceptions to this rule.

Procedures included in the protocol for the discontinuation of incorrectly enrolled patients must be followed. These procedures must take into consideration ethical and safety factors and how these patients will be treated in the analyses.

When an incorrectly enrolled patient is identified, the AstraZeneca Study Team Physician or representative and the investigator will participate in a discussion to determine whether or not to continue the patient in the study. The AstraZeneca Study Team Physician or representative will ensure all such decisions are appropriately documented.

5.4 Blinding and procedures for unblinding the study

5.4.1 Methods for ensuring blinding

The investigator, patient, and study staff will be blinded. Both AZD6765iv doses and placebo (normal saline) will be prepared as pre-mixed solutions in glass vials that must be refrigerated and should be available to the study staff on the morning of the dosing. Packaging and labeling of the IPs will be performed in a way to ensure blinding throughout the study.

No member of the study team in AstraZeneca, at study sites, or any contract research organization (CRO) handling data will have access to the randomization scheme during the conduct of the study with the exception of AstraZeneca's Investigational Product Services and Patient Safety.

The randomization schedule for blinding of randomized treatment will be maintained by AstraZeneca or representative and will not be disclosed until after database lock.

5.4.2 Methods for unblinding the study

Individual treatment codes, indicating the treatment randomization for each randomized patient, will be available to the investigator(s) or pharmacists from the IVRS/ Interactive Web Response System (IWRS). Routines for this will be described in the IVRS/IWRS user manual that will be provided to each site.

The treatment code must not be broken except in medical emergencies when the appropriate management of the patient necessitates knowledge of the treatment randomization. The investigator documents and reports the action to AstraZeneca or representative, without revealing the treatment given to the patient to the AstraZeneca or representative's staff.

AstraZeneca retains the right to break the code for serious adverse events (SAEs) that are unexpected and are suspected to be causally related to an IP and that potentially require expedited reporting to regulatory authorities. Treatment codes will not be broken for the planned analyses of data until all decisions on the evaluability of the data from each individual patient have been made and documented.

5.5 Treatments

5.5.1 Identity of investigational product

AstraZeneca or representative will supply AZD6765iv as either AZD6765 Solution for Infusion, 0.5 mg/mL (for the 50 mg dose) or AZD6765 Solution for Infusion, 1.0 mg/mL (for the 100 mg dose) as a ready to use iv solution in infusion bottles containing 100 mL (Table 5). Also, matching placebo infusion bottles of 100 mL will be supplied.

Handling instructions will be provided to the site regarding administration.

AZD6765iv or placebo must be infused using an infusion pump.

Table 5 Identity of investigational products

Investigational product	Dosage form and strength	Manufacturer
AZD6765 Solution for Infusion (AZD6765iv)	0.5 mg/mL solution for infusion 100 mL	
AZD6765 Solution for Infusion (AZD6765iv)	1.0 mg/mL solution for infusion 100 mL	
Placebo (0.9% saline)	100 mL solution for infusion	

The batch numbers will be recorded in the Study Master File and identified in the clinical study report.

5.5.2 Doses and treatment regimens

Patients will be randomized to receive 1 of the following treatments: Treatment A (AZD6765iv 50 mg), Treatment B (AZD6765iv 100 mg), or Treatment C (placebo saline) by iv infusion in a 1:1:1 ratio. Patients should be semi-recumbent in a bed or reclining chair such that their feet are at the same level as their torso during the iv infusion.

- **Treatment A:** Patients will receive AZD6765iv 50 mg (total dose) intravenously once per dosing day at the study site. The infusion will be a final volume of 100 mL given at an infusion rate of 1.67 mL/min (0.833 mg/min) over 60 minutes.
- **Treatment B:** Patients will receive AZD6765iv 100 mg (total dose) intravenously once per dosing day at the study site. The infusion will be a final volume of 100 mL given at an infusion rate of 1.67 mL/min (1.667 mg/min) over 60 minutes.
- **Treatment C:** Patients will receive placebo (0.9% saline) intravenously once per dosing day at the study site. The infusion will be a final volume of 100 mL given at an infusion rate of 1.67 mL/min over 60 minutes.

Patients will receive multiple infusions of AZD6765iv (50 mg or 100 mg) or placebo during the treatment period. The AZD6765iv dose assigned will be used for all infusions for any given patient.

5.5.3 Additional study drug

No additional study medication will be supplied by AstraZeneca or representative for this study.

5.5.4 Labeling

AstraZeneca or representative will provide the IP to the study sites. Labeling of the IPs will be performed in accordance with Good Manufacturing Practice (GMP) and local regulatory guidelines. The labels will fulfill GMP Annex 13 requirements for labeling. Label text will be translated into local language. Investigational products will be provided in labeled vials.

All clinical study material will be labeled with the drug name, study reference number, and storage conditions. It is the responsibility of the investigator to ensure that accurate accountability records are maintained throughout the study. The study site dispensary staff will dispense the IP according to the IVRS.

5.5.5 Storage

All IPs must be kept in a secure place under appropriate storage conditions. The IP label on the vial specifies the appropriate storage.

5.6 Concomitant and post-study treatments

5.6.1 Concomitant medications

Medications prohibited or permitted with restrictions are specified in [Table 6](#).

Antidepressant medications must follow the guidelines provided in [Section 3.1](#).

Any non-excluded medication that is considered necessary for the patient's safety and well-being, may be given at the discretion of the investigator. The administration of all medications (including IPs) must be recorded in the appropriate sections of the source documentation and electronic case report form (eCRF). The patient must be instructed to report all medications taken in addition to those prescribed by the investigator.

Serum lithium concentration

Serum lithium concentrations for patients receiving lithium as adjunct therapy for the treatment of their MDD will be measured as part of the clinical chemistry assessment at time points specified in [Table 4](#). Additional assessments may be performed as needed. In addition to serum lithium concentration levels, sampling dates and dosing history prior to the sampling should be recorded (ie, date and approximate time of drug intake for the 2 prior doses, captured as accurately as possible, based on the patient's memory/or notes). Lithium dosing

may be reduced after screening at the investigator's discretion only if serum lithium values are above the therapeutic range. Lithium dosing should otherwise remain unchanged.

All prior treatments for depression will be collected on the ATHF. Medications used for other indications up to 60 days prior to screening will be recorded in the appropriate sections of the source documentation and eCRF.

Table 6 Concomitant medications that are prohibited, allowed with restrictions, or permitted

Use category	Type of medication	Details
Prohibited	MAOIs	A 4-week washout prior to screening is required.
	VNS, ECT, TMS, deep brain stimulation	VNS ECT, or TMS within 6 months at randomization is exclusionary; however, VNS, ECT, or TMS history >6 months would qualify as prior therapy and is acceptable for the purposes of the ATHF.
	lamotrigine	A 2-week washout prior to randomization is required.
	valproate	A 2-week washout prior to randomization is required.
	topiramate	A 2-week washout prior to randomization is required.
	opiates	A 2-week washout prior to randomization is required.
	carbamazepine	A 4-week washout prior to randomization is required.
	memantine	A 4-week washout prior to randomization is required.
	ketamine	Prohibited within the last 6 months at randomization.
	barbiturates	A 2-week washout prior to randomization is required.
	bupropion >300 mg	All formulations at this dose are prohibited after randomization. Dose adjustment to non-exclusionary levels must be done prior to randomization.

Table 6 Concomitant medications that are prohibited, allowed with restrictions, or permitted

Use category	Type of medication	Details
Permitted with restrictions	benzodiazepines (stable dose)	
Benzodiazepines are permitted only if the patient has been taking a stable regimen and dose at least 4 weeks prior to randomization. The dosage in the past 4 weeks should be no more than lorazepam maximum dose 2 mg/day or equivalent, which includes the following:
 
 • Alprazolam 1.0 mg/day • Estazolam 4.0 mg/day • Oxazepam 30 mg/day • Temazepam 60 mg/day • Clonazepam 1.0 mg/day • Diazepam 10 mg/day 
It should be noted this is not an exhaustive list.

	Hypnotics	
One of the following medications can be used for insomnia at the restricted and maximum allowable dose of:
 
 • Zolpidem tartrate 10 mg • Ambien CR 12.5 mg • eszopiclone 3 mg • zopiclone 7.5 mg • chloral hydrate 1 gram • zaleplon 20 mg, or • ramelteon 8 mg (in the evening) 
up to the specified dosage per night if treatment has been ongoing on a regular basis since 4 weeks prior to randomization.

Permitted	Stable psychotherapy	Ongoing for at least 3 months at randomization.
	Nonpsychoactive medications, including over-the-counter medications	

Table 6 Concomitant medications that are prohibited, allowed with restrictions, or permitted

Use category	Type of medication	Details
	Nonpsychopharmacologic medications with psychotropic properties	May be used upon discussion with Sponsor or Sponsor's representative with appropriate washout prior to randomization.
	Medications required to treat illnesses or complaints that occur during the study	May be used at the discretion of the investigator.
	Medications that are considered necessary for the patient's safety and well-being	May be given at the discretion of the investigator. Includes medication and devices for contraception.
	Other permitted drugs and treatments not counted toward 3 inadequate responses	Includes other psychoactive drugs indicated for attention deficit hyperactivity disorder (eg, atomoxetine, etc) or anxiety (diphenhydramine, etc).

5.7 Treatment compliance

The administration of all IPs (AZD6765iv and placebo) should be recorded in the appropriate sections of the eCRF.

Treatment compliance will be assured by supervised administration of the IPs by the investigator or his/her designee. The investigator will query the patient to assess antidepressant therapy treatment compliance.

5.7.1 Accountability

The study drug provided for this study will be used only as directed in the study protocol.

The study personnel will account for all study drugs dispensed to and returned from the patient.

Study site personnel and the [REDACTED] monitor will account for all study drugs received at the site, unused study drugs and for appropriate destruction. Certificates of delivery, on-site destruction or return to Fisher, should be signed by the investigator or designee.

5.8 Discontinuation of investigational product

If the patient is discontinued from IP, the scheduled study visits, data collection, and procedures should continue according to the study protocol until study closure. Alternatively, if the patient does not agree to this option, a modified follow-up through regular telephone contacts or a contact at study closure should be arranged, if agreed to by the patient and in

compliance with local data privacy laws/practices. The approach taken should be registered in the eCRF.

Patients may be discontinued from IP in the following situations:

- Patient decision. The patient is at any time free to discontinue treatment, without prejudice to further treatment
- AE
- Severe non-compliance to study protocol

5.8.1 Procedures for discontinuation of a subject from investigational product

A patient that decides to discontinue investigational product will always be asked about the reason(s) and the presence of any AEs. If possible, they will be seen and assessed by an investigator. Adverse events will be followed up (See Sections 6.4.3 and 6.4.4).

If a patient is withdrawn from study, see Section 5.9.

5.9 Withdrawal from study

Patients are at any time free to withdraw from the study (IP and assessments), without prejudice to further treatment (withdrawal of consent). Such patients will always be asked about the reason(s) and the presence of any AEs. If possible, they will be seen and assessed by an investigator. Adverse events will be followed up (see Sections 6.4.3 and 6.4.4).

Patient-specific reasons for discontinuing a patient are:

- Voluntary discontinuation by the patient who is at any time free to discontinue the patient's participation in the study, without prejudice to further treatment
- Severe non-compliance to protocol
- Incorrectly enrolled patients
- Patient is lost to follow-up
- The patient has a clinically significant or serious AE that would not be consistent with continuation in the study, as determined by the investigator, AstraZeneca or representative, or the patient
- Safety reasons as judged by the investigator, particularly if patient becomes pregnant
- The condition under investigation worsened

- The patient is unable to comply with the restrictions on the use of concomitant medications as detailed in Section 5.6.1
- The patient is unable to tolerate the assigned dose of IP

Specific reasons for discontinuing a patient from the optional genetic research when genetics is a secondary objective of the study are:

- Withdrawal of consent for genetic research. A patient may withdraw from this optional genetic research at any time, independent of any decision concerning participation in other aspects of the main study described in this protocol. Voluntary discontinuation by the patient will not prejudice further treatment.

If a patient discontinues from the study before randomization, then no further follow-up will be expected. However, if the patient discontinues after randomization, but before receiving any study treatment, the patient will be asked to return for the scheduled follow-up visits through Week 10 (inclusive) for AEs and concomitant medication assessments.

If a patient discontinues from the study before completion and has received at least 1 dose of IP, the patient will be asked to return for scheduled study-related visits for the remainder of the study. If they discontinued during Weeks 1 to 3 when there are 3 scheduled visits per week, they will only be asked to return to the site once a week. The following assessments will be obtained at each visit: MADRS, CGI-S, CGI-I, C-SSRS, AEs, and concomitant medications according to the schedule displayed in Table 4 whenever possible. Every effort should be made to follow up with patients who discontinue from the study prior to Week 12. If patients refuse to return to the clinic for the study-related assessments, a modified follow-up through, for example, regular telephone contact or a contact at study closure should be arranged, if agreed to by the patient and in compliance with local data privacy laws/practices. If the patient refuses follow-up, the reason for the refusal and last contact date should be documented in the eCRF and source documents.

The investigator must notify AstraZeneca or representative of any hospitalization. Hospitalization is an SAE and should be reported as described in Sections 6.4.2 and 6.4.4. If a patient is hospitalized, the AstraZeneca safety review group will decide if the patient is to be discontinued from the study. Should the patient need to be discontinued from the study, all assessments and procedures required at Week 14 in Table 4 will be conducted.

Patients who discontinue from the study will not be replaced.

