Building upon the results of the positive NMDA clinical studies in MDD, AstraZeneca began its clinical investigation of AZD6765, a moderate affinity non-selective NMDA antagonist in treatment refractory MDD patients. The results of the single dose, proof-of-principle (Phase IIa) study, conducted as a monotherapy agent in patients with a history of inadequate response to antidepressants, showed comparable efficacy as those observed in previous studies with ketamine and CP-101,606, a NR2b antagonist, without the psychotomimetic effects. Following the results of the Phase IIa study, AstraZeneca conducted the Phase IIb study in severely depressed, highly refractory patients who had failed multiple medications in the past. The study was conducted in the adjunct setting, and utilized repeat dosing of AZD6765. Similar to the NMDA studies described above, the Phase IIb study demonstrated robust efficacy. Many of the patients in this study had an inadequate response to 3 or more

antidepressants in the past and were not deriving sufficient benefit from their current regimen of antidepressants. A similar population will be studied in this clinical study.

AZD6765 risk is based on previous clinical experience and non-clinical safety and toxicology studies. The spectrum of potential risks could include mild, transient elevations in BP, transient dizziness, and less frequent episodes of orthostatic hypotension. The clinical relevance of embryofetal developmental toxicity seen in rats and rabbits and neuronal vacuolation and degeneration seen at high doses (125 mg/kg) in rats is unknown. However, to mitigate any potential risks or embryofetal toxicity, all women of childbearing potential (WOCBP) will be required to use approved birth control measures and test negative on a urine pregnancy test prior to each infusion of AZD6765. To date, there has been no evidence of long-lasting neurological sequelae or cognitive impairment in the ≥ 500 subjects and patients who have received AZD6765. In order to further document the safety of AZD6765 in this regard, we plan to conduct cognitive testing in this study.

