3.1.3 Follow-up Visit

As implemented by Amendment 2, patients will be scheduled for a 14 (\pm 4 days)-day follow-up visit (Week 14) from last dosing to collect laboratory measurements and other assessments as detailed in [Table 4](#), including CogState.

Patients who have completed the infusions prior to implementation of Amendment 2, but are still within the 14 (\pm 4 days)-day window from last dosing, will have a 14 (\pm 4 days)-follow-up visit (Week 14), regardless of whether they have completed assessments scheduled for Week 13 (Visit 17) under the previous protocol amendment. Patients who have completed assessments scheduled for Week 13 (Visit 17) under the previous protocol amendment do not need to repeat any laboratory assessments.

Patients who have completed the infusions and are outside the 14 (\pm 4 days)-day window from last dosing at the time of implementation of Amendment 2 will be considered complete. These patients may return to the site for an unscheduled follow-up visit at the discretion of the investigator.

Table 4 Study assessments through the treatment period

	Enroll- ment		Treatment Period															
	Screen/ Washout	R															EOT	Follow- up ^b
Visit	1 ^a	2	3	4	5	6	7	8	9	10	11	12	13	14	15	16		
Infusion		1	2	3	4	5	6	7	8	9	10	11	12	13	14	15		
Week	-6 to -1	Week 1			Week 2			Week 3			W4	W5	W6	W8	W10	W12	W14	
Day (±x days)	-42 to -1	non-consecutive days									(±2)	(±2)	(±2)	(±4)	(±4)	(±4)	(±4)	
Informed consent	X																	
Inclusion/exclusion criteria	X	X																
Demography	X																	
Psychiatric (including number of depressive episodes) and family history	X																	
Prior and concomitant medication	X	X	X	X	X	X	X	X	X	X	X	X	X	X	X	X	X	
Medical and surgical history	X																	
Alcohol and drug history	X																	
ATHF	X																	
Employment status	X	X															X	
Vital signs (supine)	X	X ^c	X ^c	X ^c	X ^c	X ^c	X ^c	X ^c	X ^c	X ^c	X ^c	X ^c	X ^c	X ^c	X ^c	X ^c	X ^c	
Orthostatic BP ^d		X	X	X	X	X	X	X	X	X	X	X	X	X	X	X		
Physical examination		X															X	

Table 4 Study assessments through the treatment period

	Enroll- ment		Treatment Period															
	Screen/ Washout	R															EOT	Follow- up ^b
Visit	1 ^a	2	3	4	5	6	7	8	9	10	11	12	13	14	15	16		
Infusion		1	2	3	4	5	6	7	8	9	10	11	12	13	14	15		
Week	-6 to -1	Week 1			Week 2			Week 3			W4	W5	W6	W8	W10	W12	W14	
Day (±x days)	-42 to -1	non-consecutive days									(±2)	(±2)	(±2)	(±4)	(±4)	(±4)	(±4)	

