12.2.6 Handling of missing data

Despite efforts to minimize missing data in the design and conduct of this study, the problem of missing data is unavoidable in any MDD study due to patient dropout. Based on the previous Phase II study of D6702C00009 data, estimates for dropouts in the current study are approximately 14% by Week 6 and an additional 10% dropout by Week 12. These missing data will have some impact on the efficacy. The degree of the impact on the efficacy analysis will depend on the analysis method used, dropout reasons, amount and pattern of missing data, and the magnitude of expected treatment effect.

To mitigate the effect of dropouts on the efficacy analysis, the proposed analysis plan includes multiple layers to capture as complete a dataset as possible. First, patients will be asked to return to the clinic to collect primary and key secondary endpoint measures for the intended study period of 12 weeks even after the patient discontinues the study in order to provide the most complete dataset possible of all randomized patients. This retrieved dropout information will be included in the main efficacy analysis. Second, the reasons, proportions, and timing of patient withdrawal from the study for each treatment group will be carefully collected and adequately described and presented to help evaluate the scale of the missing data. Third, a MMRM analysis is proposed for the primary analysis. The MMRM is considered as a method of handling missing data, which does not employ explicit imputation. The MMRM methods provide a valid approach in the case that data are missing at random (MAR). The MAR is a less restricted assumption than the most restricted missing completely at random (MCAR) assumption upon which last observation carried forward (LOCF) and complete case analysis are based.

Nevertheless, missing not at random (MNAR) can never be ruled out. As indicated in regulatory guidelines and published literature that all methods require untestable assumptions because the “missingness” mechanism involves assumptions about the relationships among variables with missing values and results often vary depending on the assumptions made about

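### Sections 3.1.3, 5.8 and 5.9 do not agree on the safety follow-up of early discontinuers, and the 5.9 list leaves out CogState, laboratory tests, weight and physical examination

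*Protocol*

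**What the plan says.** Four rules in the protocol bear on what is measured after an early stop.

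- **Section 5.9, general rule.** It covers this case: "If a patient discontinues from the study before completion and has received at least 1 dose of IP". The patient is asked back for the remaining visits (once a week if the stop falls in Weeks 1 to 3), and "The following assessments will be obtained at each visit: MADRS, CGI-S, CGI-I, C-SSRS, AEs, and concomitant medications".
- **Section 5.9, hospitalization.** If a hospitalized patient has to be discontinued, "all assessments and procedures required at Week 14 in Table 4 will be conducted". Section 6.4.2 repeats this in the same context.
- **Section 5.8.** If only IP is stopped, "the scheduled study visits, data collection, and procedures should continue according to the study protocol until study closure".
- **Section 3.1.3.** A follow-up visit is set at 14 (±4) days "from last dosing to collect laboratory measurements and other assessments as detailed in" Table 4, and CogState is named among them. The visit is labelled Week 14.

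Section 2.3 makes change in cognition on CogState, and safety by laboratory measures, stated objectives. Section 1.4 refers to neuronal vacuolation and degeneration in rats at high doses, of unknown clinical relevance, and to the absence so far of lasting neurological or cognitive effects. It then says: "In order to further document the safety of AZD6765 in this regard, we plan to conduct cognitive testing in this study". Section 12.2.6 expects dropout of "approximately 14% by Week 6 and an additional 10% dropout by Week 12", and explains the return visits by the need to collect the primary and key secondary efficacy measures.

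**The concern.** The return visits in 5.9 were designed to complete the efficacy data. The safety measures that are taken only a few times in the trial were not carried over. Adverse events and severe non-compliance are reasons for stopping under both 5.8 and 5.9, and 5.9 adds inability to tolerate the assigned dose. The same event can therefore lead to the full schedule or to six items, depending on whether the site records a stop of IP or a discontinuation from the study.

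At stake are the CogState, laboratory and weight summaries. If patients leave for reasons connected with tolerability and these measures are then not taken, the comparison with placebo rests on a selected group. It cannot be repaired afterwards, because the values were never collected.

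**Working it through.** **1. When the measures are scheduled (Table 4; Section 6.4.6 for the physical examination).**

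| Measure | Scheduled after baseline | On the 5.9 list |
|---|---|---|
| CogState | Week 6, Week 14 | No |
| Hematology, chemistry, urinalysis | Week 6, Week 14 | No |
| Weight, physical examination, serum pregnancy test | Week 14 only | No |
| MADRS, CGI-S, CGI-I, C-SSRS, AEs, concomitant medication | Repeatedly | Yes |

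By the 5.9 list, a patient who leaves before Week 6 has none of the first two rows after baseline. One who leaves before Week 14 has none of the third, although Section 11.2.3 plans change in weight and BMI to Week 14 and the proportion gaining at least 7%.

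**2. Which rule applies to an early discontinuer.**

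| Situation | Assessments stated |
|---|---|
| Stops IP only (5.8) | Full schedule |
| Discontinued after hospitalization (5.9, 6.4.2) | Week 14 set of Table 4 |
| Discontinues from the study otherwise (5.9) | Six items |
| Any patient, 14 days from last dose (3.1.3) | Laboratory tests, CogState and other Table 4 items; early discontinuers neither included nor excluded |

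Section 3.1.3 treats 14 days from last dosing and Week 14 as the same visit. That holds for a patient last dosed in Week 12 (12 + 2 = 14). For a patient last dosed in Week 2 it would fall at about Week 4 (2 + 2), ten weeks before Week 14. The text does not say which is meant.

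**3. How many patients could be affected.** The base is the planned sample size (Section 12.3). With a difference of 5.5, SD 10 and one-sided alpha 0.0125, power from the noncentral t distribution is 0.8988 at 83 per arm and 0.9025 at 84, so the planned 84 is reproduced. Allowing for 10% loss, 84 / 0.90 = 93.3, rounded up to 94 per arm, and 3 × 94 = 282. The point uses this only as a denominator.

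- By Week 6: 0.14 × 282 = 39.5, about 39 patients (0.14 × 94 = 13.2 per arm).
- By Week 12: 0.14 + 0.10 = 0.24; 0.24 × 282 = 67.7, about 68 patients (0.24 × 94 = 22.6 per arm).

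These counts cover dropout for any reason. The protocol does not split them by intolerance, by stop of IP versus discontinuation from the study, or by hospitalization. They are therefore upper bounds on the numbers lost through the 5.9 list by those weeks. No dropout figure is given for Weeks 12 to 14.

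**The case against.** The case for leaving the text alone has several parts.

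- Section 5.8 already keeps patients who stop IP, including for an adverse event, on every procedure, and hospitalized patients who are discontinued get the Week 14 set. A reader might infer that everyone who stops after dosing goes without these tests. The documents do not support that: the short list applies only to discontinuation from the study.
- Section 3.1.3 is not limited to completers, so the visit 14 days after the last dose may already cover early leavers. This is possible but not stated. Its transitional rules speak of patients who have completed the infusions, and 5.9, which addresses discontinuers directly, gives the shorter list.
- Harms are not invisible. Adverse events are collected at each return visit, unresolved ones are followed as medically indicated (6.4.3), and clinically meaningful laboratory abnormalities are followed up (6.4.5). This covers harms that are noticed. It does not supply the scheduled change-from-baseline data that the cognition objective rests on.
- A light visit helps to bring back people who are leaving. That is a fair reason for a short list at every visit, and less of a reason against one fuller visit.

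A reader might also extend the point to ECG, vital signs and urine pregnancy tests. That does not hold. No ECG is scheduled after Visit 16 for anyone, and post-dose ECGs are taken at Visits 2 and 4. Vital signs are taken around every infusion, so dosed patients should have post-baseline values. Urine pregnancy tests are tied to dosing.

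**Conclusion.** The point stands as an inconsistency with a specific possible data loss. Sections 3.1.3, 5.8 and 5.9 together do not settle which safety assessments an early discontinuer has. On the 5.9 list, CogState, laboratory, weight and physical examination data after discontinuation can be selectively missing in relation to tolerability and to how the site classifies the stop.

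The size is bounded and not estimated: at most about 39 of 282 patients (14%) by Week 6 and 68 (24%) by Week 12, assuming that the protocol's all-cause dropout figures apply and that 5.9 is read literally.

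A reader might conclude that the safety objectives are answered mainly in patients who tolerated the drug, or that the comparison is biased toward safety. The documents do not show either. They give no dropout rate for intolerance, and worsening of the condition is also a reason for discontinuation, so loss of worsening placebo patients could push the other way.

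**What to change.** Reconcile Sections 3.1.3, 5.8 and 5.9 so that one kind of stop leads to one stated set of assessments. Say in 3.1.3 whether the visit 14 days from last dosing applies to early discontinuers.

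In 5.9, extend the existing sentence on the Week 14 assessments of Table 4 from hospitalized patients to every patient who discontinues after at least 1 dose and agrees to attend. Do this once, and name CogState, laboratory tests and weight as included. Keep MADRS before CogState and the other added assessments, apart from the self-report scales that Section 6.3.1 already places first. No additional ECG is needed.

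The cost is amendment wording and one fuller visit, with a 12 to 15 minute CogState battery (Section 6.4.9.5), a blood draw and an examination, for at most about 68 patients by Week 12. They are already asked to return, though some will refuse, so not all the data would be recovered. The downside is that the longer visit may deter a few patients from coming back.
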